Month 2 contact will take place 60 days (± 14 days) after receipt of dog. If at the month 1 post-pairing visit the dog trainer was satisfied that the Veteran and dog had bonded and that there were no concerns, this contact will be by telephone. If the dog trainer had concerns, this visit will take place in the participant's home. Further, if there is a child living in the home who is aged between 5 and 10 years, a home visit will be conducted regardless of the month 1 visit findings. The dog trainer will evaluate the behavior of the dog when the child is present preferably through direct observation. If this is not possible (child at school, or elsewhere) the participant will be thoroughly interviewed instead. Regardless of form of contact, the Dog Related Questions will be completed. If there is a home visit, the Veteran and Service/Emotional Support Dog Visit Report will also be completed. The participant will be reminded about the Veterinary Checklist if not already received. Participants will receive \$10 for their time and effort.

Post Pairing Outcome Visits

- **Months 3, 9 and 15 clinic visits and associated telephone calls:**

At months 3, 9 and 15 (± 14 days) after receipt of dog, the participant will attend a visit at the local VA study site. The C-SSRS, HERC non-VA care WPAI, and Medication Log will be completed in interview format. The WHO-DAS 2.0, PCL-5, PSQI, VR-12, PHQ-9, and DAR will be completed in pen and paper format. Participants will receive \$25 for each visit for their time and effort. Secondary contact information will be verified. At Months 03 and 09 the participant will be provided with the Veterinary Checklist packet (includes form 23). Each visit will last approximately 2 hours, with the exception of the month 15 visit which will be longer due to the additional steps listed below.

Month 15 Visit:

- CAPS will be administered.
- Veterinary Checklist packet (includes form 23) will be provided and should be completed around 17 Months.
- Discussions related to keeping or returning the study dog at the end of the study will be initiated.

Within approximately 2-weeks of each clinic visit, the dog trainer will telephone the participant to complete the Dog Related Questions form.

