Checklists not returned by the designated due date will require follow up with the participant and veterinarian (as needed) to verify that the exam has been completed and retrieve the missing checklist. If follow up attempts to retrieve missing forms are unsuccessful site staff will contact the CVMO in a timely manner.

- **Public observation of study dogs**

Public observations will be completed for all paired participants (SD and EMOT) at 2 separate times in the study. Sites will use their discretion to conduct the observations either at a required visit or by meeting the participant during a scheduled public outing that can be on a different date than a required post pairing visit. Public observations will occur at least 6 months apart.

- ***Ad Hoc* study Visits**

The investigator, local dog trainer, national dog trainer or local study team member may schedule an *ad hoc* visit for any study participant at any time that he/she feels such a visit is advisable to evaluate either the participant, dog, or residence. Any such visits will be documented per approved procedures as detailed in the associate study operations manual. Examples of reasons for *ad hoc* visits include supporting the training needs, changes in residence, or when a dog, or other pet is introduced into the home that may interfere with the study dog bonding relationship with the participant. The Suitability to Have a Dog Checklist, Veteran and Service Dog Visit Report, and Dog Related Questions can be administered at the discretion of the dog trainer.

Visit completion schedules: When required, visits can be initiated and completed on different dates. If this occurs the completion visit should take place within 2-weeks of the date it was initiated and must be completed within the designated early and late date window of time (i.e., \pm 14 days). This does not apply to Post Pairing Weeks 1 & 2 visits as these have limited amount of time between visits. If holiday schedules or an unusual circumstance such as veteran illness prevents the visit within the designated time frame listed above, they should be completed as soon as possible.

- **Participant Study Completion**

- Participants are considered to have completed the study if he or she has successfully completed the 18 month visit and all study related activities.

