Relatedness involves an assessment of the degree of causality (attributability) between the study intervention and the event. The assessment provided by the site investigator is part of the information used by the sponsor to determine if the adverse event presents a participant safety concern. Pursuant to CSP Global SOP 3.6, an AE is deemed to be associated with the use of a study intervention if "[t]here is a reasonable possibility that the experience may have been caused by the intervention or by participation in the trial." Thus, all adverse events with a reasonable causal relationship to the study intervention should be considered "related". A definite relationship does not need to be established. The following levels of relatedness will be used in this trial:

- Not attributed to a study intervention (study dog)
- Possibly attributed to a study intervention (study dog)
- Attributed to a study intervention (study dog)

Only possibly related or related events must be reported on a study form.

2. Adverse Event Definitions for Animals

The USDA Animal Welfare Act Regulations (AWAR) and Public Health Service Policy on the Care and Use of Animals in Research ("PHS Policy") govern animal research involving dogs. All VA-funded animal research must also comply with the rules and policies utilized by the accrediting body for animal research, which is the Association for Assessment and Accreditation of Laboratory Animal Care (AAALAC). VA policy incorporating these federal and accrediting standards is found in ORD Handbook 1200.07, Use of Animals in Research (11/23/2011), and ORO Handbook 1058.01, Research Compliance Reporting Requirements (11/15/2011; primarily paragraph 8).

Cumulative reporting requirements for IACUCs are found in VHA Handbook 1200.07, item 8.i, which lists the following categories of reportable deficiencies applicable to this study. These include (a) serious or continuing non-compliance with PHS Policy (including any serious deviation or continuing non-compliance with the provisions of the Guide, as required by the PHS Policy) or USDA AWAR, and (b) suspensions of protocols previously approved or suspensions of procedures or studies never given approval.

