2. Distress from interviews or questionnaires: Information collected on the questionnaires and interviews may upset the participant. To mitigate this risk, interviewers will allow plenty of time for the participant to answer questions and will offer breaks as necessary. The data collector may recommend that the participant contact his/her mental health provider to help with feelings.
 - In the event that a participant is distressed during questionnaire/interview completion he/she should be given the option to terminate the visit

immediately. If the participant is open to it, the visit may be continued on another occasion. The occurrence of this will be documented through the differing dates on CRFs received by PPCSPCC. The data collector may recommend that the participant contact his/her mental health provider to help with feelings.

- If the LSI and members of the local study team consider continued study participation to be too distressing for a participant they may choose to terminate the participant from the study. Decisions regarding termination from the study will be made by the LSI, and members of the local study team on a case-by-case basis.
3. **Financial Risk.** Because the well-being and medical/surgical insurance taken out on each dog by VA pays 100 percent of eligible veterinary costs with no co-pay or out-of-pocket expenses to the participants, and because all participants will receive \$75 per month for incidental expenses plus a coupon for dog food that should cover food costs, financial risk is considered to be low for participants while in the study. However, once participants complete the study, they will be responsible for all dog care and veterinary costs, which has been disclosed in the ICF.
 4. Additional risks include the loss of sensitive information. The study team will do everything possible to prevent this from occurring.
 5. Participants will be informed as soon as possible if additional risks are identified as a result of participating in this study.

- **Benefits for study**

Participants will be notified that the study team cannot promise that he/she will receive any benefits from taking part in this research study. The participant will also be told that he/she may gain benefits by interacting with the dog received.

XIV. HEALTHCARE UTILIZATION & EMPLOYMENT/PRODUCTIVITY ANALYSIS

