#### 3.2 Screening and Home/Baseline Visits

Following initial screening for inclusion criteria, participants will sign the consent form and will begin the screening visits of the study. During this visit, inclusion criteria will be verified by performing the Clinician Administered PTSD Scale for DSM 5 (CAPS-5) and the M.I.N.I. International Neuropsychiatric Interview. Within approximately one week of the screening visit, a home visit will occur to assess the home environment and to verify it is safe for a dog. During the home visit, or within approximately one week, the baseline assessment on functioning, mental health, psychosocial well-being and socioeconomic and health care utilization will be given.

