## 8 ADVERSE EVENTS

An Adverse Event (AE) can be any unfavorable or unintended sign (including an abnormal laboratory finding), symptom, or disease temporally associated with the study interventions. For the purposes of this study, the study interventions are 1) being paired with a Service Dog and 2) being paired with an Emotional Support Dog. In this study, information on AEs related to or possibly related to study intervention, for the participant, participant family members or the study dog, and on all serious adverse events (SAEs) will be collected and recorded.

Adverse events will be recorded during screening, observation phase and during the 18 months of follow-up. The reporting period for AEs begins when the participant signs the informed consent form and continues until the earlier of the 30 days after the participant's completion or early termination of study participation or the end of the study. All adverse events with a reasonable causal relationship to the study intervention should be considered "related". A definite relationship does not need to be established. The following levels of relatedness will be used in this trial:

- Not attributed to a study intervention (study dog)
- Possibly attributed to a study intervention (study dog)
- Attributed to a study intervention (study dog)

Only possibly related or related events must be reported on a study form.

Incidence of adverse events will be summarized for each treatment group by body system and MedDRA term. The number and percentage of participants with each body system and MedDRA term will be presented for each treatment group. Tables to summarize the incidence rates will be created for each of the following groups:

- Adverse events
- Adverse events by relationship to treatment
- Adverse events leading to premature discontinuation
- Adverse events presented in descending order of frequency by MedDRA term (no System Organ Class shown)
- Serious adverse events
- Serious adverse events by type
- Serious adverse events by relationship to treatment

Adverse events that led to premature discontinuation from the study will be listed. Serious adverse events will also be listed. These listings will contain details about the adverse event such as intensity and relationship to study treatment. All adverse events will be coded with MedDRA (updated version).

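### Differing CRF dates cannot reliably identify non-serious interview distress, and the printed relatedness levels name only the study dog although the definition also covers trial participation

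*Protocol*

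**What the plan says.** **Recording of distress.** Protocol XIII, Risks to subject, item 2, recognises that interviews and questionnaires may upset participants. A distressed participant may end the visit at once. Resumption is optional: "If the participant is open to it, the visit may be continued on another occasion". The next sentence is "The occurrence of this will be documented through the differing dates on CRFs received by PPCSPCC". That item names no form, tick box or reason field for the distress itself.

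**Other sources of a second date.** Protocol X, Visit completion schedules, says: "When required, visits can be initiated and completed on different dates". It excepts only the Week 1 and Week 2 visits. Protocol X, on the Month 3, 9 and 15 clinic visits, adds: "Within approximately 2-weeks of each clinic visit, the dog trainer will telephone the participant to complete the Dog Related Questions form". SAP 3.2 allows a gap at baseline as well: "During the home visit, or within approximately one week, the baseline assessment" is to be given.

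**Relatedness.** Protocol XIII, Collection of Safety Information, treats an AE as associated when there is a reasonable possibility that it "may have been caused by the intervention or by participation in the trial". It then lists three levels, each naming the dog in brackets; the middle one begins "Possibly attributed to a study intervention (study dog". SAP 8 repeats the levels and adds: "Only possibly related or related events must be reported on a study form". The protocol carries the same sentence. Both documents define the study interventions as being paired with one or the other type of dog.

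**Serious events.** Protocol XIII sends every serious adverse event (SAE) to an SAE form, including those classed as not related.

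**The concern.** The protocol identifies a specific risk in a PTSD population and then relies on a trace that other permitted conduct also leaves and that some distressed participants do not leave at all. The safety tables would be the natural second source, but a site that follows the printed levels has no level for harm caused by an interview.

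Two things are at stake. First, the AE summaries in SAP 8 may understate non-serious harm from study procedures, and those summaries are central to the safety review on which the Data Monitoring Committee (DMC) bases any termination recommendation (Protocol XVIII, Criteria for Study Termination; SAP 5.5.1.1). Second, SAP 2.3.1 initially sets the WHODAS 2.0 summary score to missing when any domain score is missing, so a visit cut short can cost a primary outcome value. SAP 5.3 plans sensitivity analyses under missing-at-random and missing-not-at-random assumptions. Stopping because of distress is a plausible non-random reason, so it would help to have that reason on file.

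**Working it through.** No stated figure needs to be reproduced. The check sets the provisions side by side.

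**Step 1. What differing dates can show.**

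| Situation | Second date on the visit's forms? | Distress present? |
|---|---|---|
| Stopped for distress, resumed on another day | Yes | Yes |
| Stopped for distress, never resumed | No | Yes |
| Distressed, but finished the same day | No | Yes |
| Split for another reason (Protocol X) | Yes | No |
| Baseline assessments after the home visit (SAP 3.2) | Yes | No |

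A second date appears with and without distress, and distress occurs with and without a second date. The marker is therefore neither specific nor sensitive. Its error rates cannot be calculated, because the documents give neither a distress rate nor a split-visit rate.

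**Step 2. What the AE route requires.**

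- Definition (Protocol XIII): causation by the intervention or by trial participation. Interview distress fits the second limb.
- Levels (Protocol XIII and SAP 8): not attributed, possibly attributed or attributed, each to the study dog. Interview distress fits only the first.
- Filter (both documents): a form is mandatory only for the second and third levels.

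On the definition, a non-serious event caused by an interview is reportable. On the printed levels, it need not be reported. The documents do not say which governs.

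**Step 3. The period before pairing.** AE reporting opens at consent (Protocol XIII). The CAPS and C-SSRS interviews take place at the Clinic Qualifying Visit, where consent is obtained (Protocol VII). The observation phase then lasts at least three months. SAP Table 1 makes the AE form available at the screening, baseline and clearing visits, and Protocol XIII plans a separate analysis of pre-randomization safety data. No study dog is present in this period, so the dog-only levels leave no participant event that must be reported unless it is serious.

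**Step 4. Exposure.** The outcome questionnaires are scheduled at Baseline 1, Baseline 2 and six follow-up visits: 2 + 6 = 8 sessions per completer. For 220 paired participants without attrition this is 8 × 220 = 1,760 sessions. If 25% were lost before any follow-up visit, it would be 165 × 8 + 55 × 2 = 1,430. These figures count occasions on which distress could arise; they do not measure harm.

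**The case against.** The sentence about dates directly follows the one about continuing the visit, so it may be meant only to document the split visit, for which differing dates are a valid record. That reading is fair. It leaves the distress itself with no named record in that item, so the gap remains.

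Several stronger readings are tempting, and the documents do not support them.

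- *That such events cannot be reported or counted at all.* The definition covers trial participation, so a site could class interview distress as related. The mandatory-form sentence sets a minimum and forbids nothing. Distress that meets the SAE criteria is reported regardless of relatedness.
- *That up to half of follow-up visits would be falsely flagged.* Months 3, 9 and 15 are three of the six outcome visits, but their second date comes from a separate telephone form completed by the dog trainer. A check limited to the participant questionnaires would not pick it up, and what remains is splits of unknown frequency.
- *That illness or holidays are given as reasons for splitting a visit.* That sentence in Protocol X concerns visits that miss their time window.
- *That procedure-related harm never reaches the DMC.* The committee also sees missed visits, completeness of follow-up and protocol breaches (Protocol XIX). It receives SAEs and may ask for whatever else it needs (SAP 5.5.1).

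The case report forms and operations manual are not part of the documents. A reason field may exist on the deviation or termination form. The point is limited to what the protocol and SAP specify.

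**Conclusion.** The point holds for non-serious events. Differing CRF dates cannot reliably identify interview or questionnaire distress. Separately, the dog-only relatedness levels conflict with a definition that includes trial participation. A site following the levels need not report non-serious harm from study procedures, and this is clearest before pairing. Any resulting under-reporting cannot be quantified from the documents. No effect on sample size, type I error or power is shown, and an effect on the primary analysis through missing scores is plausible but unmeasured.

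SAP 8 also has a smaller inconsistency. It promises to record all SAEs, yet its related-only sentence is not limited to non-serious events. The protocol's SAE section settles the intent, so this needs only a clarification.

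The conclusion assumes that sites classify events by the printed levels and that no form outside these documents already captures the reason for a stopped visit. It is a correction worth making to safety recording, not an obstacle to the trial.

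**What to change.** 1. In Protocol XIII (relatedness) and SAP 8, reword the three levels to refer to the study dog or trial participation/procedures, with a tick for which, so that they match the definition.
2. In SAP 8, show procedure-related events in a separate row of the AE summaries.
3. In Protocol XIII, Risks to subject, item 2, replace reliance on dates with a recorded reason: visit stopped for distress (yes/no) and resumed (yes/no). Use the AE form when the event meets the AE definition; this also covers distress that did not stop the visit.
4. In SAP 8, state that the related-only filter applies to non-serious AEs, consistent with the protocol's SAE section.

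The cost is wording in two sections, one tick on the AE form and two yes/no items. There will be a few more AE records and a slightly higher reported AE count; the separate row keeps dog-related counts readable. Nothing in participant management changes.

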Limitation on activity is defined as the inability to fully engage in important life domains, such as cognition, mobility, self-care, and participation in society. For all the hypotheses listed below we will examine change over the 18 month intervention period between the two groups of participants with PTSD: those who are assigned to receive a Service Dog and those who are assigned to receive an Emotional Support Dog.

Hypothesis 1a: Compared to Veterans who receive an Emotional Support Dog, Veterans who receive Service Dogs will have improved ability to fully engage in important life domains over time as measured by the WHO-DAS 2.0 domain scores and the WHO-DAS 2.0 total score.

Hypothesis 1b: Compared to Veterans who receive an Emotional Support Dog, Veterans who receive Service Dogs will have improved quality of life, as measured by the global mental and physical health component scores of the VR-12.

- **Secondary Objectives**

Objective 2: To examine how mental health is impacted by the provision of a Service Dog versus an Emotional Support Dog.

Hypothesis 2a: Compared to Veterans who receive an Emotional Support Dog, Veterans who receive a Service Dog will have reduced PTSD symptom severity, as assessed by the PCL-5

Hypothesis 2b: As compared to Veterans who receive an Emotional Support Dog, Veterans who receive a Service Dog will have decreased thoughts of suicide, as assessed by the Columbia-Suicide Severity Rating Scale (C-SSRS).

Hypothesis 2c: Compared to Veterans who receive an Emotional Support Dog, Veterans who receive a Service Dog will have a decrease in depression as assessed by the PHQ-9.

Hypothesis 2d: Compared to Veterans who receive an Emotional Support Dog, Veterans who receive a Service Dog will have improved sleep outcomes as measured by the Pittsburgh Sleep Quality Index (PSQI)

Objective 3: To characterize and compare how health care utilization and costs are affected by the provision of a Service Dog or Emotional Support Dog.

Hypothesis 3a: Compared to Veterans who receive an Emotional Support Dog, Veterans who receive a Service Dog will have lower health care utilization as quantified by inpatient and outpatient visits to healthcare providers and to mental health providers.

Hypothesis 3b: Compared to Veterans who receive an Emotional Support Dog, Veterans who receive a Service Dog will have decreased medication usage as assessed by the medical record.

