VA administrative data sets will be the source of health care utilization. The hospital discharge data and the outpatient encounters datasets available from the VA Corporate Data Warehouse will be used to characterize health services used by participants. National data extracts of the Decision Support System (DSS) will be used to characterize the cost of care. VA to determine the cost of every hospital stay, patient care encounter, uses this cost system and other service dispensed to patients. Data will come from the DSS discharge, outpatient visit, and outpatient prescription extracts. The DSS data system has been in use at all VA sites for more than 10 years, and the vast majority of encounters are assigned cost estimates that are consistent with private sector costs for similar services (Barnett & Rodgers, 1999). A very small number of DSS cost estimates (much less than 1%) are inconsistent with the expected cost given the characteristics of care. Inconsistent cost estimates will be identified by comparing the DSS data to the encounter level cost estimates in the average cost database created by the Health Economics Resource Center (Barnett, 2003; Phibbs et al, 2003; Wagner et al, 2003). HERC estimates the cost of VA health care counters based on the average cost of similar encounters in the non-VA sector. HERC cost estimates will be substituted for the 1% extremes of DSS data that are inconsistent with expected costs.

Inpatient care will be considered related to mental health if the stay was in a specialized mental health bed section, or if the primary discharge diagnosis was a mental health disorder (an ICD-9 code in the range between 290 and 390). Outpatient care will be considered related to mental health if the visit was to psychiatric clinic stop code or was characterized by any mental health diagnosis code.

Mental health medications will be identified using the VA medication class variable which is used to characterize medications in the DSS pharmacy data. We will classify as mental health medications: anti-depressants (CNS600-CN699), anti-psychotics (CN700-CN799), and other classes of medications used in treatment of PTSD. We will work with site investigators to develop a list of medications being prescribed for sleep disorders at study sites, include off-label use of low-dose anti-depressants.

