There will be an 18-month period during which to recruit 220 total study participants. There are numerous exclusion criteria that will limit participant eligibility, along with the availability of service and companion dogs. Furthermore, the numerous study procedures that will be required are labor intensive and will be time consuming for the site investigators and local study coordinators. This limits the number of participants that reasonably can be followed at any one medical center. We feel that a three-site study in which each site is expected to consent approximately 100 participants in order to obtain the overall goal of 220 pairings is realistic and highly feasible. We should easily be able to meet recruitment and follow-up goals with three participating medical centers.

- **Available Participants at each of the three proposed sites**

Three sites have been selected. Each site has provided an estimate of the potential participant population that could potentially be recruited. It was not possible to determine how much of the population at each site met all inclusion/exclusion criteria.

1. VA Portland Health Care System
[name]
[name]

Between June 1, 2012 and May 31, 2013 the VA Portland Health Care System (VAPHCS) PTSD Treatment Team (PCT) recorded 10,712 encounters with 1549 unique Veterans, for an average of 129.1 unique Veterans diagnosed with PTSD per month receiving treatment services from the VAPHCS PCT over that time interval.

2. Atlanta VA Medical Center
[name]
[name]

In Atlanta, there are approximately 40 consults per week seen (160 consults per month). Using FY13 data to this date (Oct 2012-June 2013), staff provide services to: 816 unique Veterans per month in the 540 (individual) stop code and 250 unique Veterans per month in the 561 (group treatment) stop code. There is probably some, but not total, overlap between these two, so it is reasonable to estimate 1000 unique Veterans per month are seen by the by the Atlanta VAMC PTSD Treatment Team.

3. Iowa City Veterans Affairs Health Care System
[name]
[name]

Iowa City Veterans Affairs Health Care System fields 3800 unique Veterans with PTSD per year of which 10% are referred to PTSD orientation. During FY13 (10/1/12-9/30/13) there were 3792 unique visits for patients coded with 309.81 POSTTRAUMATIC STRESS DIS.

- **Study Management**

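### The inpatient mental-health rule in Protocol XIV uses ICD-9 codes 290 to 390, a range that appears to run past the mental-disorder codes and would misclassify some stays in the secondary utilization and cost analysis

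*Protocol*

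**What the plan says.** Protocol section XIV (Healthcare Utilization & Employment/Productivity Analysis) sets the rules that sort VA care into mental-health and other care.

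- **Inpatient, first limb.** "Inpatient care will be considered related to mental health if the stay was in a specialized mental health bed section". This limb does not depend on any diagnosis code.
- **Inpatient, second limb.** Alternatively, the stay counts if the "primary discharge diagnosis was a mental health disorder (an ICD-9 code in the range between 290 and 390").
- **Outpatient.** The visit counts if the "visit was to psychiatric clinic stop code or was characterized by any mental health diagnosis code". No numeric range is given.
- **Medications.** The mental-health classes are "anti-depressants (CNS600-CN699), anti-psychotics (CN700-CN799), and other classes of medications used in treatment of PTSD".

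In Protocol section III, Hypothesis 3a is "lower health care utilization as quantified by inpatient and outpatient visits to healthcare providers and to mental health providers", and Hypothesis 3b is "decreased medication usage as assessed by the medical record". Both are secondary. SAP 7.2.2 assigns the utilization and cost analyses to the health economics group and sends the reader to the protocol for detail. Neither document restates or corrects the ICD-9 range.

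**The concern.** The second inpatient limb puts one concept into two forms that may not agree: a mental health disorder in words, and a span of codes in numbers. A programmer building the extract will work from the numbers. If the span goes beyond the mental-disorder block, a stay on a general ward with a primary diagnosis from a neighbouring block enters the count as a mental-health admission.

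The same rule applies to both arms, so this would not by itself favour one arm. If the added stays are unrelated to the type of dog, they would pull the inpatient mental-health comparison toward no difference. They would also move cost from other care into mental-health care. In addition, the inpatient rule would then be wider than the outpatient rule, which refers only to mental health diagnosis codes, although both feed the mental-health part of Hypothesis 3a.

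**Working it through.** The plan states no figure here that can be reproduced. No sample size, power or alpha depends on this rule. The check has four parts.

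**1. Width of the range.** Input from Protocol XIV: 290 to 390, both ends included.

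- Three-digit categories in the range: 390 − 290 + 1 = 101.
- Categories past the end of the mental-disorder block, if the block ends at category E: 390 − E.

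E is an assumption, because the documents do not give it.

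| Assumed end E | Inside the block (E − 290 + 1) | Past the block (390 − E) | Share of 101 |
|---|---|---|---|
| 319 | 30 | 71 | 70.3% |
| 389 | 100 | 1 | 1.0% |
| 390 | 101 | 0 | 0% |

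The point rests on the first row. The other rows show how far the count depends on the boundary, which one look at the ICD-9-CM table would settle. These are counts of code categories, not of stays.

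**2. Does narrowing the range lose PTSD?** The only specific ICD code in the documents is in Protocol XIX, in the Iowa City recruitment estimate: "patients coded with 309.81 POSTTRAUMATIC STRESS DIS". Category 309 lies within 290-390 and also within 290-319, so PTSD stays are kept under either range.

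**3. Where the range acts.**

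| Quantity | Uses 290-390? |
|---|---|
| Total inpatient and outpatient visits (3a) | No |
| Outpatient mental-health visits (3a) | No: stop code or any mental health diagnosis code |
| Inpatient stays in a mental health bed section (3a) | No: they qualify by bed section |
| Inpatient stays elsewhere (3a and related cost) | Yes |
| Medication usage (3b) | No |
| WHO-DAS 2.0, PCS, MCS | No |

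**4. Size of the effect.** Let m be the share of all stays that are for mental disorders, and f the share of the remaining stays with a code in the excess part of the range. The share of counted stays that do not belong is f(1 − m) / [m + f(1 − m)]. The documents give neither m nor f. As illustrative assumptions:

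- m = 0.60, f = 0.03: 0.012 / 0.612 = 2%.
- m = 0.15, f = 0.10: 0.085 / 0.235 = 36%.

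If the added stays have a rate ratio of 1 and the true ratio is assumed to be 0.70, the observed ratio is 0.70 + 0.30 × share. That gives 0.706 at the low end and 0.809 at the high end. The spread comes entirely from assumed inputs. It shows the direction and that the effect could be trivial or noticeable, but it is not an estimate for this trial.

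**The case against.** The strongest objection is that the ICD-9 chapter boundary is not in the documents, so the overreach cannot be shown from them alone. That is correct, and the boundary is therefore carried as a labelled assumption. It does not dispose of the point, because the protocol itself names the code set as its operative rule and the boundary can be looked up there.

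A second objection is that the verbal definition governs and the range is only a parenthetical gloss. A careful analyst might read it that way. But the range is the only numeric instruction for inpatient diagnoses, and the SAP supplies no other.

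A third is that the reach is small: part of one secondary hypothesis, through stays outside mental health bed sections only. The regressions under Economic Outcome Measures in Protocol XVIII also name no separate mental-health model. This stands and limits the weight of the point.

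A reader might infer more in three places, and the documents do not support it.

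- **Hypothesis 3b is misclassified too.** It is worded as medication usage overall, and nothing makes the mental-health class list its endpoint.
- **The antidepressant class is empty.** Read as a literal text range, `CNS600` sorts after `CN699`, so none of the 100 codes CN600 to CN699 would be selected. But the adjacent `CN700-CN799` and the word for the class make the intended range plain. This is a typing slip.
- **Every stay that qualifies only by diagnosis is missed because discharges are coded in ICD-10.** The study-flow figures are dated 2016, but neither document states the coding version during follow-up. This harm also cannot fall on the same stay as the overreach, which requires an ICD-9 code.

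**Conclusion.** The point holds in a limited form. On the assumption that the ICD-9-CM mental-disorder block is 290-319, the written rule counts some stays that are not for mental disorders as mental-health care. It does so only for stays outside a mental health bed section, and so only within the inpatient mental-health component of Hypothesis 3a and its associated cost. The 71 of 101 categories measures the excess width of the rule. The number of stays affected, and any change in the arm comparison, cannot be derived from the documents. The primary analyses and the sample size do not depend on this rule. It is worth correcting because it is the only specification for this split, and because a definition settled before extraction cannot be chosen after the results are seen.

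**What to change.** In Protocol XIV, or in an economic analysis plan that SAP 7.2.2 can cite:

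1. Check the mental-disorder block against the ICD-9-CM code table, then replace the inpatient range 290 to 390 with 290-319.
2. State the equivalent mental-disorder block for any stays coded in a later ICD version.
3. As a clerical correction only, change `CNS600-CN699` to `CN600-CN699`.

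All three should be done before the extract is run. The cost is a few words and a look at the code tables. No new data, visits or change to the primary analysis are needed.
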